6. Structural damage within 0.5 disc diameter of the center of the macula in the study eye likely to preclude improvement in visual acuity following the resolution of macular edema, including atrophy of the retinal pigment epithelium, subretinal fibrosis, laser scar(s).
7. Patients with both, a BCVA score of > 73 letters and a central subfield thickness (CSFT) of < 300 µm in the study eye.
8. Uncontrolled glaucoma in either eye at screening (IOP > 24 mmHg on medication or according to investigator's judgment).
9. Neovascularization of the iris in either eye.
10. Vitreous hemorrhage impairing the adequate diagnosis of DME in the study eye
11. Evidence of clinically relevant vitreofoveal adhesion in the opinion of the investigator, vitreofoveal traction with foveal involvement or epiretinal membrane with foveal involvement in the study eye that is likely to prevent improvement of BCVA loss due to DME.
12. Proliferative vitreoretinopathy in study eye
13. History of retinal detachment, retinal tear or macular hole in the study eye.
14. Neovascularization covering an area of \geq 2 disc areas within the macula (defined as area with 6mm diameter centered on the fovea), originating either from neovascularization of the disc or multiple neovascularization's elsewhere in study eye
15. Patients who are monocular or have a BCVA score in the non-study eye (fellow eye) < 24 letters (approximate Snellen equivalent of 20/320) at Visit 1.

Prior and planned Ocular treatments

16. Any intraocular surgery in the study eye within 4 months prior to randomization.
17. Vitrectomy/vitreoretinal surgery
 - a. In the medical history or planned for study eye
 - b. planned vitrectomy or vitrectomy in last 3 months in fellow eye
18. Planned medical or surgical intervention during the 12-months study period likely to interfere with study schedule or outcomes.

19. Panretinal laser or focal/grid laser photocoagulation in the study eye within 3 months prior to randomization unless sufficient documentation of laser photocoagulation in that period of time is available.
20. Treatment with anti-angiogenic drugs (pegaptanib sodium, anecortave acetate, bevacizumab, ranibizumab, VEGF-Trap, etc.)
 - within 3 months prior to randomization for study eye
 - within 1 month prior randomization for fellow eye.
21. Use of other investigational drugs at the time of enrollment, or within 3 months or 5 half-lives from enrollment, whichever is longer.

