## 3 Sample size calculation

A sample size of 133 patients per treatment arm will have 90% power to establish non-inferiority at a margin of 4 letters for the 0.5 mg ranibizumab “at investigators discretion” dosing regimens in comparison to 0.5 mg ranibizumab PRN in the mean average change in BCVA based on a one-sided 0.025 significance level, assuming a treatment difference of 0 letters, a SD of 10 letters and an underlying normal distribution for an unstratified t-Test (nQuery Advisor 7.0).

The Phase III study (RESTORE) results in the FAS suggest a mean average change in BCVA of 6 letters with a SD of about 7-8 letters for ranibizumab. To account for some more variability related to the re-treatment concepts and subgroup treated with additional PRP laser in this study as compared to RESTORE, a SD of 10 letters is assumed. To account for some drop outs 150 patients will be randomized per treatment arm.

As outlined in the study protocol, section “Summary of protocol amendments” (study protocol version no.1 including Amendment 1); further recruitment of patients into this study was revised and reduced. New and relevant scientific evidence regarding treatment patterns with ranibizumab was published which did not justify continuing the trial with newly included

patients. Therefore recruitment was terminated at the time when 135 patients were enrolled into the study, resulting in a reduced sample size present for analysis.

As a consequence results are to be interpreted in a purely descriptive manner. With an estimate of about 120-150 patients to be enrolled by end of recruitment the expected power would be about 55-60% and will be evaluated accordingly.

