### 5.3 Rule of exclusion criteria of analysis sets

**Table 5-4 Protocol deviations that cause subjects to be excluded**

Deviation ID	Description of Deviation	Exclusion from Analyses
I00	Not signed Informed Consent	Excluded from all analysis
I01	Subject is less than 18 years of age or age missing.	Not reportable
I02aa	Patients with diabetes but type of diabetes is not known.	Not reportable
I02ab	Patient with no History of diabetes.	Excluded from PP analysis
I02b	Glycosylated hemoglobin greater than 12 percent, i.e. 107 mmol per mol Hb, at screening Visit 1	Reportable
I03a	Patients without visual impairment due to DME in the study eye	Excluded from PP analysis
I03b	Patients without visual impairment due to DME in the fellow eye	Not reportable
I04a	BCVA less than 24 in the study eye, using ETDRS-like visual acuity testing charts at a testing distance of 4 resp. 1 meters (approximate Snellen equivalent of 20/32 to 20/320) at screening or baseline	Not reportable
I04b	BCVA greater than 78 in the study eye, using ETDRS-like visual acuity testing charts at a testing distance of 4 resp. 1 meters (approximate Snellen equivalent of 20/32 to 20/320) at screening or baseline	Excluded from PP analysis
I05	Concomitant conditions in the study eye, which prevent improvement of visual acuity on study treatment	Excluded from PP analysis (medical review)
E01aa	Active intraocular inflammation grade trace or above in the study eye at enrollment.	Excluded from PP analysis (medical review)
E01ab	Active intraocular inflammation grade trace or above in the fellow eye at enrollment.	Not reportable
E01a	Women who are pregnant or breast feeding.	Not reportable
E02	Any active infection in either eye at the time of enrollment e.g. conjunctivitis, keratitis, scleritis, endophthalmitis.	Reportable (medical review)
E03	History of uveitis in either eye at any time.	Not reportable
E04	Structural damage within 0.5 disc diameter of the center of the macula in the study eye likely to preclude improvement in VA, incl. atrophy of RPE, subretinal fibrosis, laser scar(s).	Excluded from PP analysis (medical review)
E05	Patients with both, a BCVA score of greater than 73 letters and a central subfield thickness of less than 300 micro meter in the study eye.	Excluded from PP analysis (medical review)
E06	Uncontrolled glaucoma in either eye at screening. IOP greater than 24 mmHg on medication or according to investigator judgment.	Excluded from PP analysis (medical review)

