E07	Neovascularization of the iris in either eye.	Not reportable
E08	Vitreous hemorrhage impairing the adequate diagnosis of DME in the	Excluded from

Deviation ID	Description of Deviation	Exclusion from Analyses
	study eye.	PP analysis
E09	Clinically relevant vitreofoveal adhesion, vitreofoveal traction or epiretinal membrane with foveal involvement likely to prevent improvement of BCVA, according to investigator opinion.	Not reportable
E10	Proliferative vitreoretinopathy in study eye.	Not reportable
E11	History of retinal detachment, retinal tear or macular hole in the study eye.	Not reportable
E12	Neovascularization covering an area greater than or equal to 2 disc areas within the macula defined as area with 6mm diameter centered on the fovea for study eye.	Not reportable
E13	Patients who are monocular or have a BCVA score in the non-study eye less than 24 letters approximate Snellen equivalent of 20 per 320 at Visit 1.	Not reportable
E14	Any intraocular surgery in the study eye within 4 months prior to randomization.	Reportable (medical review)
E15a	Vitrectomy/vitreoretinal surgery - In the medical history or planned for study eye.	Reportable (medical review)
E15b	Planned vitrectomy or vitrectomy in last 3 months in fellow eye.	Not reportable
E16	Planned medical or surgical intervention during the 12 months study period likely to interfere with study schedule or outcomes.	Reportable (medical review)
E17	Panretinal or focal or grid laser photocoagulation in study eye within 3 months prior to randomization unless sufficient documentation of laser photocoagulation in that period of time is available.	Reportable (medical review)
E18a	Treatment with anti-angiogenic drugs within 1 month for fellow eye prior randomization.	Not reportable
E18b*	Treatment with anti-angiogenic drugs within 3 months (84 days) for study eye prior randomization.	Excluded from PP analysis
E19	Use of other investigational drugs at the time of enrollment, or within 3 months or 5 half-lives from enrollment, whichever is longer.	Reportable (medical review)
E20	History of intravitreal corticosteroid treatment in phakic study eye.	Reportable (medical review)
E21	Intravitreal corticosteroids in post-cataract surgery study eye (aphakic or pseudophakic, without damaged posterior capsule) within 3 months or 6 months for dexamethasone implant (Ozurdex®) or 3 years for fluocinolone implant (Iluvien®) prior to randomization.	Excluded from PP analysis

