E22	Ocular conditions in the study eye that require chronic concomitant therapy with topical ocular corticosteroids.	Reportable (medical review)
E23	Stroke less than 4 months prior to screening.	Not reportable
E24	Renal failure requiring dialysis or renal transplant.	Not reportable
E25	Untreated diabetes mellitus.	Not reportable
E26	BP defined as systolic value of greater than 160 mm Hg or diastolic value greater than 100 mm Hg at screening or randomization.	Not reportable
E27	Conditions that require chronic concomitant therapy with systemically administered corticosteroids.	Reportable (medical review)
E28	Current use of Medications known to be toxic to the lens, retina or	Reportable

Deviation ID	Description of Deviation	Exclusion from Analyses
	optic nerve, including Deferoxamine, Chloroquine or hydroxychloroquine, Plaquenil, Tamoxifen, Phenothiazines and Ethambutol.	(medical review)
E29	Use of any systemic anti VEGF drugs within 3 months prior to Screening.e.g. bevacizumab, ziv afibbercept.	Excluded from PP analysis
E30	Known hypersensitivity to fluorescein or ranibizumab or any component thereof or drugs of similar chemical classes.	Not reportable
E31	Disease severity/medical condition/ treatment expected to progress, recur, or change to an extent may bias the assessment of clinical status of patient or special risk to a significant degree.	Reportable (medical review)
D01	MH or AE - Rhegmatogenous retinal detachment or Stage 3 or 4 macular hole in the study eye and no treatment discontinuation.	Excluded from PP analysis (medical review)
D02	MH or AE - Transient ischemic attack or a stroke during the study and no treatment discontinuation	Not reportable
D03	Pregnancy but patient not discontinued from trial.	Excluded from PP analysis
D04	Vitrectomy that did not lead to discontinuation of study treatment.	Excluded from PP analysis
S01	Patient received Ranibizumab from another study or as commercially available Lucentis	Not reportable
S02	Study task injection of ranibizumab was performed by untrained site personnel.	Not reportable
S03	Patient received study medication which was outside the allowed temperature range and should have not been used any more according to guidelines or QP decision.	Reportable (medical review)
M01	Concurrent use of any anti-VEGF agents either systemic or in the study eye (only permitted in the fellow eye).	Excluded from PP analysis

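### SAP Table 5-4 keeps E09 eyes in the per-protocol set, although I05 and E04, which rest on the same reason, lead to exclusion

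*SAP*

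**What the plan says.** SAP 5.3, Table 5-4, gives each protocol deviation a consequence for the analysis sets. Three rows turn on a study eye whose vision is not expected to improve:

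- **I05:** "Concomitant conditions in the study eye, which prevent improvement of visual acuity on study treatment". Excluded from the PP analysis, subject to medical review.
- **E04:** "Structural damage within 0.5 disc diameter of the center of the macula in the study eye likely to preclude improvement in VA". Same consequence as I05.
- **E09:** relevant vitreofoveal adhesion, vitreofoveal traction or "epiretinal membrane with foveal involvement likely to prevent improvement of BCVA, according to investigator opinion". Not reportable.

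E09 comes from exclusion criterion 11 in Protocol 4.2, which ends with "epiretinal membrane with foveal involvement in the study eye that is likely to prevent improvement of BCVA loss due to DME".

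SAP 2.6.4 gives the PPS result nearly the same weight as the FAS result, because this is a non-inferiority comparison. SAP 2.4.2 says that deviation severity and impact may still change, and that the final list is settled at the blind data review meeting (BDRM).

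**The concern.** The three rows share one rationale, but E09 has the opposite PPS consequence and the SAP gives no reason. An epiretinal membrane that prevents improvement meets both E09 and I05. With no precedence rule, the same eye can stay in the PPS under one code or go to medical review for exclusion under the other.

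The direction matters. Eyes that do not respond under either regimen pull the difference between arms towards zero, which favours a non-inferiority conclusion. The PPS is meant to guard against that, and this row leaves in it eyes that the protocol declares ineligible for this very reason.

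**Working it through.** **Step 1: compare the rows.**

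- *Source:* I05, E04 and E09 come from inclusion criterion 5 and exclusion criteria 6 and 11. All three protocol criteria concern the study eye. The E09 row omits the words for the study eye, but criterion 11 contains them, so E09 is not a fellow-eye item.
- *Rationale:* the wording is *prevent improvement* (I05), *likely to preclude improvement* (E04) and *likely to prevent improvement* (E09). E09 and E04 express the same degree of certainty.
- *Consequence:* I05 and E04 lead to exclusion after medical review. E09 carries neither exclusion nor a review flag.
- *Central reading:* the general image grading items in SAP 2.4.3 include adhesion or epiretinal membrane. They also include concomitant conditions that would prevent improvement, structural damage and vitreous hemorrhage. The matching rows for those three (I05, E04, E08) all carry PPS exclusion, so central grading does not explain the treatment of E09.

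**Step 2: reproduce the plan's own figure.** SAP 3 claims "90% power to establish non-inferiority at a margin of 4 letters" with 133 patients per arm, "based on a one-sided 0.025 significance level, assuming a treatment difference of 0 letters, a SD of 10 letters".

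- The normal approximation gives 132 per arm.
- The stated unstratified t-test, computed with the noncentral t distribution, gives 133 (power 0.9015; 132 gives 0.8993).

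The figure reproduces, and the E09 issue does not affect it.

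**Step 3: size of the dilution.** The documents do not give the number of E09 eyes, so a share p is assumed. Further assumptions:

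- p is the same in both arms, and these eyes show no regimen difference at all.
- SD stays at 10.
- All 135 patients (SAP 3) are evaluable, so n = 67.5 per arm.
- The true DI minus PRN difference in the other eyes is -4, the edge of the margin.

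Formulas:

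- Observed difference: d = -4 × (1 - p).
- Standard error: 10 × √(2/67.5) = 1.721.
- Noncentrality: (4 + d)/1.721 = 4p/1.721. This is 0.046 for p = 2%, 0.116 for 5% and 0.232 for 10%.
- False non-inferiority: the chance that a noncentral t with 133 degrees of freedom exceeds the central 97.5% point.
- Power after exclusion: the same test at a true difference of 0 with 67.5 × (1 - p) per arm.

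| p | Patients of 135 | Observed difference | False non-inferiority | Power if excluded |
|---|---|---|---|---|
| 0% | 0 | -4.00 | 2.5% | 63.6% |
| 2% | 2.7 | -3.92 | 2.8% | 62.7% |
| 5% | 6.75 | -3.80 | 3.3% | 61.3% |
| 10% | 13.5 | -3.60 | 4.2% | 59.0% |

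The 63.6% counts every patient as evaluable. With the plan's own allowance (133 of 150 retained) it becomes 58.3%, inside the 55-60% that SAP 3 states.

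**Step 4: scale.** The 95% confidence interval half-width is about 3.4 letters (1.96 × 1.721 = 3.37). A shift of 4 × 0.02 = 0.08 to 4 × 0.05 = 0.20 letters is small beside it.

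**The case against.** The strongest replies, and what stands of each:

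- *Exclusion under I05 and E04 is not automatic, and a patient can have several deviations.* True. An E09 eye may also be coded I05 and reach medical review that way. But nothing in the table requires the second code, and E09 alone gives the review no prompt.
- *The list is provisional until the BDRM.* True, and this limits severity. It makes the BDRM the place to correct the row but does not justify its present content.
- *Such eyes should be rare.* Probably so. Randomization needs reading-centre confirmation of the diagnosis (Protocol 5.3), and the screening OCT is read centrally for eligibility (Protocol 6.4.2). The 10% line in the table has no support in the documents.
- *Likely is not certain, and an eye that cannot gain letters can still lose them.* Correct. No regimen difference in E09 eyes is an assumption. If these eyes respond in part, the dilution is smaller.
- *The study is exploratory.* Yes, but SAP 2.6.2 still runs the test and keeps a rule for claiming non-inferiority.

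A reader might infer two stronger points that the documents do not support:

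- *That E09 breaches disappear from the report.* SAP 2.4.2 summarizes all deviations by arm and lists them, so they remain visible.
- *That rows E15a and D04 show the same inconsistency for vitrectomised eyes.* E15a, "Vitrectomy/vitreoretinal surgery - In the medical history or planned for study eye", is an entry breach. It includes surgery only planned and is already flagged for medical review. D04, "Vitrectomy that did not lead to discontinuation of study treatment", is study treatment continued against the discontinuation rule in Protocol Table 5-1, a different deviation. The table draws the same line between E11 (history of detachment, tear or macular hole, not reportable) and D01 (on-study detachment or hole without discontinuation, excluded after review). No passage says that vitrectomised eyes cannot gain vision.

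**Conclusion.** The inconsistency between E09 and the pair I05/E04 is real on the face of Table 5-4, and it can make PPS membership depend on coding. Its effect is anti-conservative but small: false non-inferiority of about 2.8% to 3.3% instead of 2.5%, if 2% to 5% of eyes in both arms cannot respond. That range rests on the assumed share, SD 10, 135 evaluable patients and a true difference of -4 letters in the remaining eyes. Severity is minor, given the exploratory status and the provisional deviation list. The point does not extend to E15a.

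**What to change.** Reclassify E09 in Table 5-4 as excluded from the PP analysis subject to medical review, matching I05 and E04. Do this masked, at or before the BDRM and before database lock. I05 and E09 then have the same consequence, so the choice of code no longer matters and no precedence rule is needed between them.

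Use the reading-centre item on vitreofoveal adhesion or epiretinal membrane (SAP 2.4.3) only to prompt the medical review. It lacks E09's conditions that improvement is likely to be prevented and that the investigator holds this opinion, so excluding on that item alone would apply a different criterion.

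The cost is one table cell, a masked review of images already graded, and a few fewer PPS patients. Under the assumptions above, power at a true difference of 0 falls from 63.6% to between 62.7% and 61.3%.
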